## Appendix 8 Summary of Treatment and Food Restrictions

[figure not shown]
Treatment	Washout Period	During Treatment	Reason
Immunosuppressants other than those allowed by protocol	30 days	Prohibited	Interferes with study efficacy endpoints
Aminoglycosides Amphotericin B Melphalan Ketoconazole Rifampin	14 days	Prohibited	May potentiate toxicity
NSAIDs chronic dosing (>7 consecutive days)	Prohibited	Prohibited	May potentiate nephrotoxicity
P-gp substrates	To be monitored	To be monitored	Drug-drug interaction
P-gp inhibitors	To be discussed with Medical Monitor	To be discussed with Medical Monitor	Drug-drug interaction
Androgenic steroids Cimetidine Fluconazole, itraconazole Macrolide antibiotics (azithromycin, clarithromycin, erythromycin) Metoclopramide Barbiturates and derivatives Carbamazepine Octreotide acetate Phenytoin Sulfadimidine (intravenous) Theophylline	To be discussed with Medical Monitor	To be discussed with Medical Monitor	Drugs interfering with Orelvo metabolism
ACE inhibitors and ARBs	No change or introduction during screening	Change or commencement prohibited	Interfere with primary endpoint assessment
Foods Grapefruit and grapefruit juice	24 hours	Prohibited	May affect the metabolism of Orelvo

[figure not shown]
Abbreviations: ACE = Angiotensin converting enzyme; ARB = Angiotensin receptor blocker; NSAID = Non-steroidal anti-inflammatory drug; P-gp = P-glycoprotein.

[figure not shown]

[figure not shown]
**Appendix 9 Short Form Health Survey (SF-36) HRQoL Assessment**

[figure not shown]

**Appendix 10 LupusPRO (v1.7) HRQoL Assessment**

---

**AMENDMENTS BEFORE DATABASE LOCK**

Version	Issue Date	Section	Revision/Addition	Rationale
2.0	Jul 2018	6.11.2.2 11	Adding additional covariate to the sensitivity analysis for the primary endpoint. Covariate will be MMF $\leq 2$ g versus MMF $> 2$ g. MMF dose to be defined as each patient's maximum dose during the study.	To assess possible differences between responses for patients taking higher levels of MMF.
2.0	Jul 2018	6.11.2.3 11	Component analysis for primary endpoint to be undertaken for both Adjudicated response and programmed response	To ensure full details of the analysis are available should differences between adjudicated response and programmed response become apparent.
2.0	Jul 2018	6.11.2.2 11	Sensitivity analysis using regional covariate will be defined at both continental and country level	To ensure sufficient information is available re: regional differences.
2.0	Jul 2018	6.11.3.3	Confirming Week 24 Renal Response will be a programmed endpoint only. This will not be adjudicated by the CEC	Ensuring consistency between the SAP and the CRC charter
2.0	Sep 2018	6.13.1	Updating assumptions for missing AE relationships	Ensure definitions are as per current requirements
2.0	Sep 2018	5 6.2.12 9	Confirming that region (used as blocking factor) will be in the primary model	Regulatory Agency feedback requesting clarification
2.0	Sep 2018	6.11.1	Adding clarification around the make-up of the CEC: blind and independent	Regulatory agency feedback
2.0	Sep 2018	6.11.1	Adding rescue medication clarifications	Regulatory Agency feedback
2.0	Sep 2018	6.11.2.1 6.11.2.2 6.11.2.3	Adding clarification around the sensitivity analyses, supplementary analyses and the tipping point analysis.	Regulatory agency feedback

2.0	Sep 2018	3.1	Clarifying that subjects who withdraw from the study are defined as non-responders	Regulatory Agency feedback
2.0	Sep 2018	3.2.1 3.2.2 9	Duration of UPCR $\leq 0.5$ moved from key secondary to other secondary	Regulatory Agency feedback
2.0	Sep 2018	1	Clarification around IV methylprednisolone	Ensure consistency with protocol
2.0	Sep 2018	6.4	Clarification withdrawal versus discontinuation	Ensure consistent use throughout the SAP
2.0	Sep 2018	6.11.3.2 6.11.3.3 6.11.4.1 6.11.4.2 6.11.4.3 6.11.4.4	Referencing baseline section for endpoints that use non-standard calculations	Ensure baseline calculations are clear for each endpoint
2.0	Sep 2018	6.13.1	Add adverse event displays using exposure-adjusted incidence rates as a summary	Regulatory agency feedback
2.0	Sep 2018	6.13.1	Changing relative risk to risk difference in overall summary of AEs table	Retain consistency between treatment comparisons given the additional exposure adjusted summary tables
2.0	Sep 2018	Various	Consistently referring to 'population' rather than 'set'	Language consistency
3.0	March 2019	3.1	Paragraph added to detail the primary estimand	Regulatory agency feedback
3.0	March 2019	6.11.2.4	Step 3 updated to make it clear that stratification variables are to be included in the model and that different data is generated for each of the 50 analyses	Regulatory agency feedback
4.0	May 2019	6.11.2.4	Tipping point analysis: imputation model brought into line with the analysis model	Regulatory feedback
4.0	May 2019	Table 14.3.8.1  Section 6.13.1	Treatment Emergent Adverse Events by Descending Frequency of Preferred Term Safety Analysis Population	Added following review

4.0	May 2019	Table 14.3.8.2  Section 6.13.1	Non-Serious Treatment Emergent Adverse Events by System Organ Class and Preferred Term  Safety Analysis Population	Added following review
4.0	May 2019	6.7 Medical History (Glossary 16.2.9.1)  6.8 Prior and Concomitant Medications (Glossary 16.2.9.2)  6.13.1 Adverse Events (Glossary 16.2.9.3)	Glossaries for medications, medical conditions and adverse events added	Added following review
5.0	Oct 2019	Section 6.2.2	Updated baseline definition for urine creatinine.	Updated following review
5.0	Oct 2019	Section 6.6	Added table for regions and countries in baseline comparability section.	Updated following review
5.0	Oct 2019	Section 6.7	Updated calculation of 'Years sinc ...' variables.	Updated following review
5.0	Oct 2019	Section 6.11.2.3	Added clarifications for eGFR success.	Updated following review
5.0	Oct 2019	Section 6.13.1	Updated definition of TEAEs to be up to last dose + 30 days. Removed detailed list of AE tables and referring to list of tables instead.	Updated following review
5.0	Oct 2019	Section 11	Updated list of tables, listings and figures based on TFL review.	Updated following review
5.0	Oct 2019	Whole document	Finalization of the text throughout the document.	

## LIST OF ABBREVIATIONS

AE	Adverse event
AURORA	AURinia Orelvo Renal Assessments
Aurinia	Aurinia Pharmaceuticals Inc.
BID	Twice daily
BP	Blood pressure
C3 / C4	Complement 3 / complement 4
CEC	Clinical Endpoints Committee
CI	Confidence interval
dsDNA	anti-double-stranded deoxyribonucleic acid
EDC	Electronic data capture
ECG	Electrocardiogram
eCRF	Electronic case report form
eGFR	Estimated glomerular filtration rate
ESRD	End-stage renal disease
HR	Heart rate
HRQoL	Health-related quality of life
ITT	Intent-to-treat
IV	Intravenous
IVC	Intravenous cyclophosphamide
IWRS	Interactive web response system
LN	Lupus nephritis
MMF	Mycophenolate mofetil
MMRM	Mixed Effect Model Repeated Measures
OR	Odds ratio
Orelvo	Voclosporin (for Phase 3 lupus nephritis indication)
PK	Pharmacokinetic
QTc	Corrected QT interval
QTcF	QT interval duration corrected for heart rate using method of Fridericia
SAE	Serious adverse event
SAP	Statistical analysis plan
SELENA	Safety of Estrogens in Lupus Erythematosus National Assessment
SLE	Systemic lupus erythematosus
SLEDAI	Systemic Lupus Erythematosus Disease Activity Index
TEAE	Treatment-emergent adverse event
UPCR	Urine protein creatinine ratio
█	█

## 1 INTRODUCTION

This document details the planned statistical analyses for the AURORA, protocol “AUR-VCS-2016-01” study titled “A Randomized, Controlled Double-blind Study Comparing the Efficacy and Safety of Orelvo (voclosporin) (23.7 mg Twice Daily) with Placebo in Achieving Renal Response in Subjects with Active Lupus Nephritis”.

The proposed analyses are based on the contents of the final version of the protocol (Amendment 1 dated 04 May 2017).

Lupus nephritis (LN) manifests as diverse patterns of immune complex-mediated renal disease affecting glomerular, tubulointerstitial, and vascular compartments. It can lead to permanent and irreversible tissue damage within the kidney, resulting in end-stage renal disease (ESRD), and thus making LN a serious and potentially life-threatening condition. In subjects with LN, renal damage results in proteinuria and/or hematuria and a decrease in renal function as evidenced by reduced creatinine clearance and estimated glomerular filtration rate (eGFR), and increased serum creatinine levels.

This is a Phase 3, multicenter, randomized, prospective, double-blind, parallel-group, placebo-controlled, 2-arm comparison study of voclosporin (herein referred to as voclosporin (VCS)) versus matching placebo. Subjects who provide a signed and dated informed consent will be screened into the study up to 30 days before randomization. During the screening period, eligibility criteria will be assessed. A kidney biopsy may be performed, provided the subject has given consent and provided the results can be obtained and reviewed before baseline. Subjects who meet all of the inclusion criteria and none of the exclusion criteria will be eligible for randomization into the study.

[figure not shown]
Baseline assessments will be performed before the first dose of study treatment is administered on Day 1. Using an interactive web response system (IWRS), eligible subjects will be randomized to receive either oral voclosporin 23.7 mg twice daily (BID) or matching placebo for 52 weeks. All subjects who weigh  $\geq 45$  kg should receive 0.5 g IV methylprednisolone on both Day 1 and Day 2 (a total of 1 g), before oral corticosteroid therapy is started on Day 3. All subjects who weigh  $< 45$  kg should receive 0.25 g IV methylprednisolone on both Day 1 and Day 2 (a total of 0.5 g). When subjects are receiving IV methylprednisolone, they should not receive oral corticosteroids on the same day. Starting at the Baseline Visit, all subjects will also receive background therapy with mycophenolate mofetil (MMF).

All subjects will return for assessment of efficacy and safety at Day 2 and Weeks 2, 4, 8, 12, 16, 20, 24, 30, 36, 42, 48, and 52. In addition, subjects not on MMF during screening, will start receiving MMF at the Baseline Visit and will return for local complete blood count assessments at Weeks 1 and 3 after randomization.

All subjects, completed or withdrawn, will complete the End of Treatment/Early Termination assessments (Visit 15) at Week 52 or at the time of early termination. Subjects who do not enroll in the planned continuation study will attend the Safety Follow-up Visit (Visit 16) at Week 56 to collect any new AEs and concomitant medications. At the follow-up visit, urine protein creatinine ration (UPCR) and estimated glomerular filtration rate (eGFR) will be assessed as well.

## 1.1 Schedule of Events

**Figure 1.1 Schema**

Notes: BID = Twice daily; IV = Intravenous; MMF = Mycophenolate mofetil.

**Table 1.1 AUR-VCS-2016-01 Schedule of Events**

Visit 	Visit 1 Screening	Visit 2 Baseline	Visit 3	Visits 4-8	Visit 9	Visit 10	Visits 11- 13	Visit 14	Visit 15 End of Treatment/ Early Termination 	Visit 16 Safety Follow-up 
Day/Week	Day -30 to Day -1	Day 1	Day 2	Wks 2, 4, 8, 12, 16 ±3 days	Wk 20 ±3 days	Wk 24 ±10 days	Wks 30, 36, 42 ±10 days	Wk 48 ±10 days	Wk 52 ±10 days	Wk 56 ±10 days
Informed consent	✓									
Eligibility criteria	✓	✓								
Kidney biopsy 			See footnote 							
Randomization		✓								
Medical/Surgical/SLE/LN history	✓									
Demography	✓									
Physical examination 	✓	✓				✓			✓	
Vital signs (BP, pulse, temperature)	✓	✓	✓	✓	✓	✓	✓	✓	✓	✓
ECG 	✓			✓ 		✓			✓	
Laboratory assessments 	✓	✓		✓	✓	✓	✓	✓	✓	✓
Pharmacokinetics 						✓			✓	
Urinalysis	✓	✓		✓	✓	✓	✓	✓	✓	✓
FMV urine collection	✓ 			✓	✓	✓	✓	✓	✓	✓
24-hour urine 	✓					✓			✓	
Pregnancy test 	✓	✓		✓	✓	✓	✓	✓	✓	
AEs		✓	✓	✓	✓	✓	✓	✓	✓	✓
Concomitant medications 	✓	✓	✓	✓	✓	✓	✓	✓	✓	✓

Visit 	Visit 1 Screening	Visit 2 Baseline	Visit 3	Visits 4-8	Visit 9	Visit 10	Visits 11- 13	Visit 14	Visit 15 End of Treatment/ Early Termination 	Visit 16 Safety Follow-up 
Day/Week	Day -30 to Day -1	Day 1	Day 2	Wks 2, 4, 8, 12, 16 ±3 days	Wk 20 ±3 days	Wk 24 ±10 days	Wks 30, 36, 42 ±10 days	Wk 48 ±10 days	Wk 52 ±10 days	Wk 56 ±10 days
SELENA-SLEDAI		✓				✓			✓	
SF-36 and LupusPro 		✓		✓ 		✓			✓	
Healthcare Resource Utilization 		✓				✓			✓	
Dispense study treatment/compliance		✓		✓	✓	✓	✓	✓	✓ 	
First dose of study treatment (at the study site) 		✓								
MMF dispensing 		✓		✓	✓	✓	✓	✓	✓	
IV methylprednisolone administration 		✓	✓							
Oral corticosteroid tapering				✓						

- 1 Unscheduled visits/assessments can be done as needed. Adverse events, concomitant medications and verbal compliance check is needed.
- 2 Subjects who discontinue study treatment or terminate the study early, are to attend an Early Termination Visit and have the assessments listed performed. Subjects who complete study treatment will attend the End of Treatment at Week 52 and have the assessments listed performed.
- 3 Subjects who do not enroll into the continuation study will have a follow up safety visit 4 weeks after the last dose of study treatment.
- 4 If a subject has not had a recent kidney biopsy, one may be performed to assess eligibility for the study provided informed consent has been given and results are received prior to randomization. If one is performed as part of standard of care after randomization, the results will be recorded in the electronic case report form.
- 5 Complete physical examination at screening, abbreviated examination at all other applicable visits. Height is measured at screening only.
- 6 During the study, and after screening, in the event that a subject is noted to have a QTcF value exceeding 500 msec, or >60 msec more than baseline, the ECG will be repeated. Electrocardiograms will be recorded digitally after the subject has been in a resting, supine position for at least 5 minutes.
- 7 Week 12 only.
- 8 Laboratory assessments will be performed according to the schedule in Section 6.13.2; subjects must be fasting for at least 8 to 12 hours at baseline and end of study/early termination.
- 9 Blood samples will be collected at 0 and 2 hours post dose on subjects who provide consent for pharmacokinetics.
- 10 Two FMV specimens, to be performed and resulted before baseline.
- 11 24-hour urine collection should begin 2 days prior to the scheduled study visit in order not to coincide with the FMV sampling due on the day of the study visit.
- 12 Serum pregnancy test to be evaluated at central laboratory at screening, Week 24, and Week 52; urine pregnancy test will be performed locally at all other applicable visits.
- 13 Concomitant medications include all herbal medicines and supplements taken by the subject.
- 14 For details on HRQoL assessments, see Section 6.11.4.8.
- 15 For details on Healthcare Resource Utilization, see Section 6.11.4.11.
- 16 Compliance only.
- 17 All scheduled procedures must be done prior to first dose, including IV methylprednisolone and MMF.
- 18 For subjects not on MMF during screening, will start receiving MMF therapy at the Baseline Visit and return for local complete blood count assessments at Weeks 1 and 3 after randomization.
- 19 IV methylprednisolone administered 0.5 g on baseline and Day 2. If IV corticosteroids must be administered during screening then the FMV urine specimens will be collected prior to the infusion.

Notes: Subjects who discontinue therapy will attend their regularly scheduled study visits to the end of the study. Subjects who withdraw consent and terminate the study early or discontinue treatment early should be advised to attend both Visit 17 and the Safety Follow up Visit (Visit 18).

Abbreviations: AE=adverse event; BP=blood pressure; CBC=complete blood count; ECG=electrocardiogram; FMV=first morning void; HRQoL=health-related quality of life; IV=intravenous; LN=lupus nephritis; MMF=mycophenolate mofetil; QTcF=QT interval duration corrected for heart rate using method of Fridericia; SAE=serious adverse event; SELENA-SLEDAI=Safety of Estrogens in Lupus Erythematosus National Assessment - Systemic Lupus Erythematosus Disease Activity Index; SLE=systemic lupus erythematosus.

## **2 STUDY OBJECTIVES**

### **2.1 Primary Objective**

To assess the efficacy of voclosporin compared with placebo in achieving renal response after 52 weeks of therapy in subjects with active LN.

### **2.2 Secondary Objective**

To assess the safety and tolerability of voclosporin over 52 weeks compared with placebo in subjects with active LN.

### 3 ENDPOINTS

#### 3.1 Primary Endpoint

Renal response at Week 52 will be adjudicated by the Clinical Endpoints Committee (CEC) based on the following parameters:

- UPCR of  $\leq 0.5$  mg/mg, and
- eGFR  $\geq 60$  mL/min/1.73 m^2 or no confirmed decrease from baseline in eGFR of  $>20\%$ , and
- Received no rescue medication for LN (see Protocol Section 7.8, Prohibited Therapy and Concomitant Treatment), and
- Did not receive more than 10 mg prednisone for  $\geq 3$  consecutive days or for  $\geq 7$  days in total during Weeks 44 through 52, just prior to the renal response assessment

The CEC will also take into account the following:

- Subjects who withdraw from the study prior to the Week 52 assessment and provide insufficient week 52 data to determine response will be defined as non-responders. Subjects who discontinue study drug but continue to attend study visits (as is the expectation) will have their data assessed for response.
- eGFR values eliminating a subject from complete remission should be accompanied by a treatment or disease-related treatment-emergent adverse event (TEAE) that impacts eGFR. Full details are given in Section [6.11.1](#).
- The CEC is independent and blinded from the treatment groups.

The primary endpoint estimand is the proportion of subjects showing renal response as adjudicated by the CEC in the ITT population when comparing voclosporin and placebo at Week 52. It is assessed in all randomized subjects who were recruited according to the inclusion/exclusion criteria of the protocol.

The variable is binary and indicates a response if a subject shows, at 1 year, adequate UPCR with no signs of detrimental impact on eGFR. Subjects who cannot be shown to be responders through their 1 year data (or absence thereof) are defined as non-responders.

Intercurrent events include:

- Treatment discontinuation for any reason
  - the subject remains on study, allowing the primary endpoint to be assessed at 1 year.
- Study discontinuation
  - resulting in insufficient information at 1 year to ascertain response status leading to assumed non-response.
- Rescue medication taken at any time prior to the primary assessment at 1 year
  - results in non-response. Rescue medication is adjudicated by the Clinical Endpoints Committee.
- Death at any time prior to the 1 year primary assessment
  - results in assumed non-response.

## **3.2 Secondary Endpoints**

### **3.2.1 Key Secondary Endpoints**

- Time to UPCR of  $\leq 0.5$  mg/mg
- Partial renal response as defined by 50% reduction from baseline in UPCR at Weeks 24 and 52
- Time to 50% reduction in UPCR from baseline
- Renal response at Week 24 (based on definition of primary endpoint)

### **3.2.2 Other Secondary Endpoints**

- Duration of UPCR  $\leq 0.5$  mg/mg
- Change from baseline in UPCR at each time point
- Change from baseline in serum creatinine, urine protein, and eGFR at each time point

- Proportion of subjects experiencing a confirmed >30% decrease from baseline in eGFR at each time point
- Change from baseline in immunology parameters (complement 3 (C3), C4, and anti-double-stranded deoxyribonucleic acid (dsDNA)) at Weeks 24 and 52
- Renal response with low-dose steroids at Weeks 24 and 52 (defined as renal response in the presence of corticosteroids of  $\leq 2.5$  mg/day between Weeks 16 to 24 and Weeks 44 to 52)
- Change from baseline in health-related quality of life (HRQoL) at Weeks 12, 24, and 52
- Health Resource Utilization at Weeks 24 and 52
- Change from baseline in the Safety of Estrogens in Lupus Erythematosus National Assessment - Systemic Lupus Erythematosus Disease Activity (SELENA-SLEDAI) Index score at Weeks 24 and 52

## 4 SAMPLE SIZE

The total sample size will be approximately 324 subjects (162 subjects per treatment arm). This is based on the following assumptions:

- A two group continuity corrected Chi square test with a 0.05 two-sided significance level will have 80% power to detect the difference between a placebo response rate of 20.0% and a voclosporin response rate of 34.4% (odds ratio=2.1) when the sample size in each group is 162 (total N=324).
- The effect of withdrawals will be investigated. Subjects withdrawing for any reason will be counted as non-responders in the primary analysis and therefore no adjustment of sample size for withdrawals is necessary.
- The impact of withdrawals on primary endpoint will be investigated in the tipping point analysis.

Table 4.1 shows the voclosporin response rates required to maintain a minimum 80% power at the planned sample size for given placebo response rates. These response rates all lead to odds ratios of around 2, which is a clinically relevant effect.

**Table 4.1 Voclosporin Response Rates Required to Maintain a Minimum 80% Power**

Placebo Response Rate	Voclosporin Response Rate	Odds Ratio
15%	28.4%	2.25
19%	33.2%	2.12
25%	40%	2.0

## **5 RANDOMIZATION**

All subjects enrolled must be identifiable throughout the study. The Investigator will maintain a list of subject numbers and subject names to enable records to be found at a later date. Subjects will be allocated a subject number at the screening visit and registered with an interactive central randomization system. Subjects meeting the required eligibility criteria will be randomized to treatment at Visit 2 (baseline).

The randomization will be stratified by biopsy class (Class V only versus Others) and by prior MMF use at time of screening. The subjects will be randomized in a ratio of 1:1 to receive either voclosporin 23.7 mg BID or matching placebo. To help ensure balance, a centralized randomization will be utilized where region will be employed as a blocking factor. This will ensure balance between treatment groups within each of the 4 regions: North America, Latin America, Europe / South Africa and Asia Pacific.

## **6 PLANNED ANALYSES**

No statistical analysis plan (SAP) prepared in advance of the data can be absolutely definitive and the final clinical study report (CSR) may contain additional tables or statistical tests if warranted by the data obtained. The justification for any such additional analyses will be fully documented in the final CSR.

### **6.1 Analysis Populations**

Subjects excluded from the analysis populations and the reason for their exclusion will be listed in Appendix 16.2.

#### **6.1.1 Screened Population**

The Screened population includes all subjects who were screened and were allocated a subject number.

#### **6.1.2 Intent-to-Treat Population**

The intent-to-treat (ITT) population will be based on ITT principles and will consist of all subjects who are randomized to treatment. This group will be analyzed based on the treatment to which the subject was randomized.

#### **6.1.3 Per-Protocol Population**

The Per-Protocol (PP) population will be a subset of the ITT consisting of those subjects who:

- Satisfy all of the inclusion / exclusion criteria
- Do not have any treatment administration errors
- Do not take prohibited concomitant medications

All protocol deviations will be assessed and documented on a case-by-case basis before the database lock and in a blinded fashion. Deviations considered to have a serious impact (major protocol violation) on the efficacy results will lead to the relevant subject being excluded from the PP population. Before database lock, potential subject exclusions from PP population will be reviewed by the Sponsor and documented in a subject evaluability document (██████████).

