### 7.8.1 Prohibited Medications

The following medications cannot be taking during the study:

- IV corticosteroids within 2 weeks prior to screening (Visit 1) unless approved by the Medical Monitor
- Enteric-coated oral corticosteroids during the study are not allowed. No other use of non-enteric coated oral corticosteroids, other than administration required as per protocol, is allowed
- IV immunoglobulin treatment within 2 weeks prior to screening (Visit 1)
- Cyclophosphamide within 4 weeks prior to screening (Visit 1)
- Cholestyramine or other drugs that may interfere with enterohepatic recirculation of MMF within 4 weeks prior to screening (Visit 1)
- Initiation of new treatment or change in dosage of ARBs and/or ACE inhibitors within 4 weeks prior to randomization (Visit 2)
- CNIs (e.g., cyclosporine and tacrolimus) within 1 month of screening (Visit 1)
- Immunosuppression biologic agents (e.g., abatacept, belimumab, infliximab, adalimumab, etanercept, or rituximab) within 3 months prior to screening (Visit 1)
- Vaccines using live organisms, viral or bacterial
- MMF dose other than 2 g/day without prior discussion with the Medical Monitor
- Concomitant therapy with other immunosuppressants after randomization, other than MMF administered per protocol
- Subjects are allowed to be on AZA or mycophenolate sodium during screening but must switch to MMF at randomization
- Current or planned use of ketoconazole or rifampin
- Concomitant use of other CYP3A4/5 inhibitors and inducers should be discussed with the Medical Monitor

[Appendix 8](#) contains a summary of additional treatment and food restrictions.

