### 6.11.2.3 Supplementary Analyses based on the Primary Endpoint

A number of supplementary analyses based around the primary endpoint will be undertaken. Different aspects of the endpoint, be they the calculation method, different data assumptions or different populations will be varied to assess the impact of each.

- Renal response at Week 52 will be derived programmatically and analyzed in an identical fashion to the primary analysis (Table 14.2.1.1.2). Using the same definition as given to the CEC and as set out in the primary endpoint section, renal response at week 52 will be derived programmatically. All components of the primary response endpoint will be independently programmed apart from the use of rescue medication. The CEC adjudication on the use of rescue medication will be incorporated into the programmed endpoint.
- The analysis described in Section 6.11.2 will be repeated for the PPS (Table 14.2.1.3).
- The analysis described in Section 6.11.2 will be repeated for each biopsy class category (Class III, Class III/V, Class IV, Class IV/V, Class V and Class VI). The combining of classes may be necessary should subject numbers in any individual class be deemed insufficient. A separate category defined as “All but Pure Class V” will be defined (Table 14.2.1.4).
- For both the adjudicated week 52 renal response (primary endpoint) and the programmed week 52 renal response (supplementary endpoint), each individual component (and some component groups) of the endpoint will be summarized by treatment group and analyzed in the same manner using a logistic regression. Analysis will be undertaken where possible, however, it is recognized that individual components may include very low numbers of subjects (either responders or non-responders). “eGFR success” is defined as an eGFR measure of  $\geq 60$  mL/min/1.73 m^2 *or* no confirmed decrease from baseline in eGFR of >20% *or* no disease-related or treatment-related AE impacting eGFR. Where data allows, the numbers of subjects achieving each of the following will be summarized (Table 14.2.1.5.1 (adjudicated) and Table 14.2.1.5.2 (programmed)):
  - UPCR  $\leq 0.5$  mg/mg

- eGFR success
- UPCr  $\leq 0.5$  mg/mg and eGFR success
- Received no rescue medication for LN
- No withdrawal prior to remission assessment

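### The per-protocol rule in SAP 6.1.3 makes no exception for lupus nephritis rescue, so it can remove rescue-treated failures from the per-protocol denominator

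*SAP*

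**What the plan says.** SAP 6.1.3 defines the PP population as a subset of ITT. One of its three conditions is that subjects "Do not take prohibited concomitant medications". A paragraph below the list adds a review step: "All protocol deviations will be assessed and documented on a case-by-case basis before the database lock and in a blinded fashion". The consequence for the PP population is then given: "Deviations considered to have a serious impact (major protocol violation) on the efficacy results will lead to the relevant subject being excluded". The section does not mention rescue.

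SAP 3.1 gives the rescue component of the primary endpoint as "Received no rescue medication for LN (see Protocol Section 7.8, Prohibited Therapy and Concomitant Treatment), and", so the reader is sent to the prohibited-therapy section of the protocol. Among the intercurrent events, the same section lists "Rescue medication taken at any time prior to the primary assessment at 1 year", which "results in non-response. Rescue medication is adjudicated by the Clinical Endpoints Committee".

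Protocol 7.8.1 includes among its prohibited medications "Concomitant therapy with other immunosuppressants after randomization, other than MMF administered per protocol", and also oral corticosteroids beyond those the protocol requires. Protocol 5.6.1 calls subjects who need rescue beyond what the protocol permits treatment failures.

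SAP 6.11.2.3 says that the primary analysis "will be repeated for the PPS". Protocol 13.8.2 lists the PP repeat as a sensitivity analysis.

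**The concern.** The same event is treated in two ways. In the ITT analysis, rescue is an outcome: the subject stays in the denominator as a non-responder. In the PP analysis, the drug that makes the subject a failure can also be the reason for removing the subject. Such an exclusion depends on the outcome, not only on adherence.

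The PP repeat is meant to show what happens when the population is restricted to subjects without major violations. If rescued failures drop out, a difference between the PP and ITT results has two possible sources, adherence and the handling of rescue, and the odds ratio alone cannot separate them. Agreement between the two is open to the same doubt.

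**Working it through.** **Inputs.** SAP section 4 gives 20.0% response on placebo, 34.4% on voclosporin, odds ratio 2.1, 162 subjects per arm, a continuity-corrected chi-square test, two-sided 0.05 and 80% power. The rescue rates below are assumptions, since neither document gives any.

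**Step 1: reproduce the planning figures.**

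- Odds ratio: (0.344/0.656) / (0.20/0.80) = 0.5244/0.25 = 2.10.
- The continuity-corrected sample size formula gives 163 per arm against 162 stated, and power at 162 per arm is 79.9%. The plan's figure is reproduced to within one subject per arm.

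**Step 2: remove rescued failures.** Let r_p and r_v be the fractions of each arm that are rescued. All are non-responders by definition of the endpoint, so the responders are untouched and only the denominators shrink:

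- PP response rate, placebo: 0.20/(1 − r_p)
- PP response rate, voclosporin: 0.344/(1 − r_v)
- OR_PP = [0.344/(0.656 − r_v)] / [0.20/(0.80 − r_p)]

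With 10% rescued in each arm, for example, the rates go from 20.0% to 0.20/0.90 = 22.2% and from 34.4% to 0.344/0.90 = 38.2%.

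**Step 3: find when the odds ratio moves.** Write f_p = r_p/0.80 and f_v = r_v/0.656 for the fraction of non-responders rescued in each arm. Then

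OR_PP = 2.10 × (1 − f_p)/(1 − f_v).

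The odds ratio changes only if f_p and f_v differ. Unequal rescue rates are not enough in themselves, and equal rescue rates do not protect it.

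**Step 4: assumed scenarios.**

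| Rescue, placebo/voclosporin | f_p / f_v | PP response rates | OR_PP |
|---|---|---|---|
| none | 0 / 0 | 20.0% / 34.4% | 2.10 |
| 10% / 5% | 0.125 / 0.076 | 22.2% / 36.2% | 1.99 |
| 20% / 10% | 0.250 / 0.152 | 25.0% / 38.2% | 1.86 |
| 20% / 20% | 0.250 / 0.305 | 25.0% / 43.0% | 2.26 |
| 5% / 10% | 0.062 / 0.152 | 21.1% / 38.2% | 2.32 |
| 10% / 8.2% | 0.125 / 0.125 | 22.2% / 37.5% | 2.10 |

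One row in full, for 10%/5%: (0.344/0.606)/(0.20/0.70) = 0.5677/0.2857 = 1.99.

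The odds ratio falls toward 1 when a larger share of placebo non-responders is rescued, and rises when a larger share of voclosporin non-responders is rescued. If rescued subjects stay in the PP population as non-responders, rescue leaves the planning odds ratio at 2.10.

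**Limits.** The calculation is unadjusted, whereas the planned model has covariates. It also assumes that every rescued subject is excluded and that nobody else is.

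**The case against.** The strongest reply is that 6.1.3 does not make exclusion automatic. Deviations are reviewed case by case, blinded, before database lock, and the decisions are recorded in a subject evaluability document that is not part of the plan. A reader might infer from the bullet alone that every rescued subject is dropped; the text does not establish that. The review does not close the gap, however. Rescue fixes the subject's primary outcome as non-response, so it readily meets a test of serious impact on efficacy. Blinding to arm does not prevent selection on outcome. No rule links the exclusion review to the rescue decisions of the Clinical Endpoints Committee (CEC).

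Second, rescue and prohibited medication overlap only in part. Protocol 7.8 does not define rescue, and the CEC may adjudicate any treatment as rescue. Many restricted items, such as live vaccines, ketoconazole or long courses of NSAIDs, are not LN rescue. This stands, and it means that the number affected is unknown.

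Third, a reader might infer that the PP odds ratio is necessarily biased, or that the response rate rises more in the arm with more rescue. Neither follows. At 10%/8.2% the odds ratio does not move. At 10%/8% the placebo rate rises by 2.2 points (20.0% to 22.2%) and the voclosporin rate by 3.0 points (34.4% to 0.344/0.92 = 37.4%), although placebo has more rescue.

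Fourth, it would be too strong to say that the PP result carries no information. SAP 6.1 lists excluded subjects with reasons, 6.4 summarizes the reasons for PP exclusion by arm, and 6.11.2.3 summarizes the no-rescue component by arm. These outputs would help a reader to judge how much of a difference comes from rescue. They describe the problem after the fact and do not remove it from the estimate.

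**Conclusion.** The point holds as a gap in the PP definition. The rule as written can remove outcome-defined failures, and nothing in either document keeps CEC-adjudicated rescue cases in the PP population. Wherever that happens, the arm's PP response rate goes up. The PP odds ratio shifts only if the fraction of non-responders rescued differs between arms.

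Direction and size cannot be derived from the documents. Across the assumed scenarios, the planning value of 2.10 becomes anything from 1.86 to 2.32, and in one of them it does not change. These figures rest on assumed rescue rates, on exclusion of all rescued subjects, and on an unadjusted calculation.

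The consequence is limited. The PP analysis is supplementary and lies outside the Hochberg procedure. The primary ITT analysis, its type I error and the sample size are not affected. This is a cheap improvement to a supporting analysis.

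**What to change.** Add to SAP 6.1.3, before the blinded review of exclusions: medication adjudicated by the CEC as LN rescue is not in itself a reason for exclusion from the PP population, and subjects who received it stay in that population as non-responders. Keep the exclusion for prohibited medication that is not adjudicated as rescue, subject to the existing blinded case-by-case review.

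The cost is one sentence. No new data are needed, because the CEC already adjudicates rescue. Compared with excluding these subjects, the PP set becomes slightly larger and the PP response rates slightly lower.
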